12.3.1. Post-Consent Eligibility Validation

Participation in the study begins with signing the informed consent as described in Section 11.1. During the screening period (see Section 12.4) eligibility for the study is assessed. If the subject does not meet the eligibility criteria, the subject will be considered a screen failure and no further follow-up will be required.

12.4. Screening

All screening assessments are to be conducted at the study site by the study staff. The tests required at screening are summarized in Table 12.1-1 and described in Sections 12.4 to 12.4.7.

If the subject is found to not meet study eligibility criteria during the screening period, including during diagnostic angiography, the subject will be considered a screen failure and should not be randomized/enrolled. A Screening Log will be maintained in the EDC system to document selected information about subjects who fail to meet the REDUCE-HTN: REINFORCE Clinical study eligibility, including the reason for screen failure.

12.4.1. Demographics and Medical History (within 50 or 21 days prior to randomization)

Demographic data (age, gender, race, etc.) will be collected within 50 days (for patients requiring wash-out) or 21 days (for patients not requiring wash-out) of randomization. A comprehensive medical history will be collected to verify inclusion/exclusion criteria.

12.4.2. Medication Wash-Out Period [a minimum of 4 weeks (28 days) prior to randomization]

All patients that meet medical history requirements and sign the study Informed Consent Form will be discontinued from current antihypertensive medications, as applicable. There will be a 4-week wash-out phase prior to randomization. If a patient is not on antihypertensive medication at the time of Informed Consent, the wash-out period is not applicable.

12.4.3. Limited Physical Examination (within 21 days prior to randomization)

A limited physical examination, including weight and height will be conducted.

12.4.4. Blood Pressure Monitoring (within 21 days prior to randomization)

12.4.4.1. Office-Based BP and Heart Rate

Office-based blood pressure measurements collected during the screening period will be used to determine whether or not the subject meets the inclusion criteria. Office-based blood pressures will be measured using an electronic sphygmomanometer (Omron HEM-705CP-II monitor (Omron Healthcare, Vernon Hills, IL, USA) according to the instructions in Section 12.1.1.1. A heart rate will be recorded at the time of each blood pressure measurement. The

office-based blood pressure measurements documenting study eligibility must be performed after the medication wash-out period if applicable and within 21 days prior to randomization.

12.4.4.2. 24-Hour Ambulatory BP Monitoring

24-hour Ambulatory BP Monitoring, during the screening period, will be used to determine whether or not subjects meet the study inclusion criteria. 24-Hour Ambulatory Blood Pressure Monitoring will be performed as outlined in the Ambulatory Blood Pressure Monitoring Core Laboratory Manual. The ABP measurement documenting eligibility must be performed after the medication wash-out period if applicable and within 21 days prior to randomization.

12.4.5. Laboratory Assessments and Calculations (within 21 days prior to randomization/enrollment)

All subjects will have screening blood assays conducted including basic metabolic panel (BMP) of sodium, potassium, calcium, chloride, bicarbonate, glucose, blood urea nitrogen (BUN) and serum creatinine. The serum creatinine (plus demographic, height and weight data) will be used to calculate an estimated glomerular filtration rate (eGFR). In addition, renin, aldosterone, HbA1c and complete blood count (CBC) with platelet count will be collected.

A urine or serum pregnancy test will be performed on all prospective female subjects of child-bearing potential within 24 hours of randomization.

12.4.5.1. eGFR Calculation

The Modification of Diet in Renal Disease (MDRD) Study¹ equation will be used to calculate the eGFR for all subjects enrolled in the study. The MDRD calculation utilizes the serum creatinine reported in mg/dL and is normalized to a 1.73 m² body surface area, which is an accepted average adult body surface area. See the definition and formula in Table 27.2-1: Definitions Table 27.2-1.

12.4.6. Non-Invasive Imaging (within 6 months prior to informed consent)

12.4.6.1. Computed Tomographic Angiography (CTA)

A computed tomographic angiography (CTA) of the kidneys must be performed using standard techniques to confirm that all anatomical inclusion criteria have been met, and that none of the exclusion criteria have been met. The CTA may have been performed within 6 months of the patient signing Informed Consent. If a CTA has not been previously performed, it is recommended that the CTA be performed once office and ambulatory BP eligibility has been confirmed.

Visual assessment will be used to determine if criteria are met. This initial anatomic assessment should be recorded in the subject medical records to document that study eligibility criteria have been met. CTA images must be sent to the angiographic core laboratory for evaluation.

NOTE: Final anatomic eligibility will be confirmed during diagnostic angiography (see Section 12.5.1.1).

12.4.7. Quality of Life Assessment (within 7 days prior to randomization)

Quality of Life (QOL) Survey: Psychological General Well-Being Index (PGWBI)²⁸ will be administered to the subject within seven (7) days prior to randomization.

12.5. Treatment Period

For the REDUCE-HTN: REINFORCE Clinical Study, subjects will be randomized to either the control group, who will receive a masked procedure or to the treatment group, who will receive renal denervation. All subjects will be washed out from antihypertensive medications and remain off medications through the primary efficacy assessment at 8 weeks post randomization unless rescue medication is required as described in Section 13.1.

12.5.1. Diagnostic Renal Angiogram, Masked Procedure and Renal Denervation Procedure

Patients meeting all clinical eligibility and anatomic eligibility based on non-invasive imaging will undergo diagnostic renal angiography. If anatomic eligibility is confirmed during the diagnostic angiogram, the patient will be immediately randomized and enrolled to the control or to the renal denervation treatment.

12.5.1.1. Diagnostic Renal Angiogram

A diagnostic aortogram should be performed to obtain visual confirmation of all renal arteries. A selective arteriogram will be performed on each renal artery using a diagnostic catheter in order to confirm anatomic eligibility is met.

NOTE: If new anatomical exclusion criteria are identified during the angiogram the patient should not be randomized.

Upon catheter/sheath removal, either manual compression or commercialized closure devices can be used to achieve hemostasis at the puncture site. Standard-of-care post-intervention monitoring procedures should be followed.

Angiographic images must be sent to the angiographic core laboratory for evaluation.

12.5.1.1.1 Diagnostic Angiogram Medications

Investigators should prescribe procedural medications consistent with current clinical practice for renal endovascular procedures. Consider pre-treatment with anxiolytic medications. Subjects must be sedated. Intra-arterial vasodilators may be administered during angiogram to prevent spasm.

Investigators should ensure close monitoring of the amount of contrast for subjects with low baseline eGFRs.

12.5.1.2. Masked Procedure

The masked procedure will consist of the diagnostic renal angiogram performed to confirm anatomic eligibility (see Section 12.5.1.1).

12.5.1.2.1 Masked Procedure Medications

Investigators should prescribe procedural medications as described for the diagnostic angiogram in Section 12.5.1.1.1.

12.5.1.3. Renal Denervation Procedure

Investigators should practice standard of care for procedures not defined in the protocol, Vessix Reduce Catheter Directions for Use (DFU) or Vessix Generator Operators Manual (OM). The DFU and OM contain more detailed Vessix Reduce Catheter preparation, Vessix Generator operation, cable connections, power algorithms and trouble-shooting instructions.

Investigators should consider placement of a Foley catheter and make additional allowances for appropriate analgesic.

12.5.1.3.1 Renal Denervation Procedure Medications

Investigators should prescribe procedural medications consistent with current clinical practice for subjects randomized to renal denervation treatment. Anti-coagulation therapy administered during the procedure should be consistent with current clinical practice for renal endovascular procedures. There is no protocol requirement for heparin reversal or antiplatelet therapy post-procedure. Investigators may consider a low dose aspirin regimen if they feel that prophylactic platelet anti-aggregation is warranted.

There is no clinical evidence to date suggesting the need for anticoagulant/ antiplatelet medications post-treatment.

Subject must be able to tolerate analgesics during the treatment. Consider pre-treatment with both anxiolytic medications and analgesic medications, such as morphine sulfate or fentanyl. Subjects must be sedated. Intra-arterial vasodilators may be administered during the procedure or prior to final angiogram after completing the procedure to prevent spasm.

Investigators should ensure close monitoring of the amount of contrast for subjects with low baseline eGFRs.

12.5.1.3.2 Renal Artery Access

- Use a femoral puncture technique to insert an appropriately sized (5 or 6F) introducer sheath. An activated clotting time (ACT) of >200 seconds is recommended prior to the initiation of the renal denervation procedure.
- The appropriate Vessix Reduce Catheter to be used for the treatment should be identified from the information in Table 12.5-1 below.

Table 12.5-1: Vessix Reduce Catheter Sizing

Recommended Catheter Sizing Table	
Artery Size	Balloon Size
3.0 - 4.0 mm	4.0 mm
3.8 - 5.0 mm	5.0 mm
4.7 - 6.0 mm	6.0 mm
5.6 - 7.0 mm	7.0 mm

- The short sheath should be exchanged for the recommended 7F guide sheath (Vessix Guide Sheath).
- Introduce a 0.014 inch or 0.018 inch guide wire into the renal vasculature via the guide sheath. The wire should be placed beyond the bifurcation. Once access is secured, the Vessix Reduce Catheter should be prepared for treatment.

12.5.1.3.3 Placement of Vessix Reduce Catheter

- Insert the Vessix Reduce Catheter over the guide wire through the sheath. If resistance is encountered, do not force passage. Resistance may indicate a problem and may result in damage to the balloon circuitry if it is forced. If significant resistance is encountered, remove and replace the Vessix Reduce Catheter.
- Advance the Vessix Reduce Catheter over the guide wire until the balloon is fully inside the renal artery, and the distal electrode is located 3 - 5 mm proximally to the first bifurcation, using direct fluoroscopic visualization. Do not torque the Vessix Reduce Catheter during insertion or placement.
- Utilize the proximal and distal electrodes on the balloon as a reference to optimally position the Vessix Reduce Catheter.

NOTE: Due to the length of the balloon catheter and average length of the renal artery, no more than two non-overlapping treatments per artery are expected.

12.5.1.3.4 Vessix Reduce Catheter Activation and RF Treatment

- Once connection to the Vessix Generator is confirmed, the Vessix Reduce Catheter can be inflated moving in 0.5 ATM increments up to a pressure of 3.0 ATM.
- When proper apposition is confirmed by the Vessix Generator upon balloon inflation, fluoroscopy should be used to demonstrate that the catheter is at the optimal position and that blood flow is occluded. Discontinue use of the Vessix Reduce Catheter if excessive pressure is required to inflate the balloon.
- Perform the denervation treatment. (See Vessix Generator Operators Manual).
- Initiate the treatment by pressing the Treat Button on the front of the Vessix Generator. (See the Vessix Generator Operators Manual).
- If the more proximal portion of the artery needs to be denervated to achieve treatment of the full length of the renal artery, avoid overlap of treatment zones. It is

- recommended that the gap between treatment zones is approximately 5mm. (**NOTE:** To allow for a partial treatment it is acceptable for the balloon to be located partially outside of the renal artery in the aorta).
- Upon completion of the treatment, deflate the balloon by 0.5 ATM decrements and carefully retract the balloon back into the guide sheath, preferably in a coaxial manner. If resistance is encountered, advance the balloon 5 to 10 mm back into the renal artery, and carefully retract the balloon again into the sheath with care to avoid drawing the sheath into the artery. The guide wire should remain in the renal artery until a selective renal arteriogram has been completed.
 - Perform post procedural imaging on the treated renal artery.
 - Treat the contralateral renal artery at this time if the Vessix Reduce Catheter is appropriately-sized. If treatment of the contralateral renal artery requires a different balloon size, remove the Vessix Reduce Catheter, and insert an appropriately sized catheter.
 - Treat accessory renal arteries at this time if study anatomical criteria are met. Ensure the Vessix Reduce Catheter is appropriately-sized. If treatment of the accessory renal artery requires a different balloon size, remove the Vessix Reduce Catheter, and insert an appropriately sized catheter.

12.5.1.3.5 Vessix Reduce Catheter Deflation and Removal

- Slowly deflate the balloon to negative pressure.
- Carefully retract the Vessix Reduce Catheter through the guide sheath and out of the body.
- Upon guide sheath removal, either manual compression or commercialized closure devices can be used to achieve hemostasis at the puncture site. Standard-of-care post-intervention monitoring procedures should be followed.

Angiographic images must be sent to the angiographic core laboratory for evaluation.

NOTE: Re-treatment with renal denervation is not allowed through the protocol follow-up period.

12.5.2. Data Collection

The following data will be collected during and after the procedure.

- Procedural times
- Device usage data
- Generator display data, including the number of electrodes activated
- Renal anatomical measurements
- Medications
- ACT – should be therapeutic at > 200 seconds once the femoral access is in place prior to the introduction of the investigational device
- Adverse events

12.6. Hospital Discharge

Prior to hospital discharge, the following will be reviewed and documented:

- Limited physical examination including height and weight
- Blood assays (serum creatinine, CBC and platelets, BMP and HbA1c)
- Office-based sitting and standing blood pressure (obtained by blinded study personnel) and heart rate
- Medications administered since last visit including medications administered during the hospitalization
- Adverse events
- Blinding index assessment

Subjects should be made familiar with the follow-up study visit schedule and instructed to report any unusual pain or symptomology, medication changes, etc. to the study Investigator between study follow-up visits. Antihypertensive medications should only be added and/or adjusted by study Investigators as described in Figure 13.2-1.

12.7. Follow-up Visit Week 2 (14 ±7 days)

The 2-week follow-up office visit (14 ±7 days) will include the following assessments:

- Limited physical exam including height and weight
- Office-based sitting and standing blood pressure (obtained by blinded study personnel) and heart rate
- Medications administered since last visit
- Adverse events

12.8. Follow-up Visit Week 4 (28 ±7 days)

The 4-week follow-up office visit (28 ±7 days) will include the following assessments:

- 24-Hour Ambulatory BP Monitoring
- Limited physical exam including height and weight
- Office-based sitting and standing blood pressure (obtained by blinded study personnel in the US) and heart rate
- Medications administered since last visit
- Adverse events

12.9. Follow-up Visit Week 8 (56 ±7 days)

The 8-week follow-up office visit (56 ±7 days) will include the following assessments:

- 24-Hour Ambulatory BP Monitoring

- Limited physical exam including height and weight
- Quality of Life Assessment
- Blood assays (serum creatinine, CBC and platelets, renin, aldosterone, BMP and HbA1c)
- Office-based sitting and standing blood pressure (obtained by blinded study personnel in the US) and heart rate
- Medications administered since last visit
- Adverse events
- Blinding index assessment

After completion of the 8-week follow-up assessments, subjects not at target (target defined as OSBP <140 mmHg) will have antihypertensive medications reintroduced as described in Section Medication Additions13.

12.10. Follow-up Visits Months 3, 4 and 5 (90 ±14 days, 120 ±14 days, 150 ±14 days)

The 3-month (90 ±14 days), 4-month (120 ±14 days) and 5-month (150 ±14 days) follow-up visits will include the following assessments:

- Limited physical exam including height and weight
- Office-based sitting and standing blood pressure (obtained by blinded study personnel in the US) and heart rate
- Medications administered since last visit
- Adverse events

After completion of the 3, 4 and 5-month OBP follow-up assessments, subjects not at target (target defined as OSBP <140 mmHg) will have antihypertensive medications adjusted or reintroduced as described in Section 13.2.

12.11. Follow-up Visit Month 6 (180 ±14days)

The 6-month follow-up office visit (180 ±14 days) will include the following assessments:

- 24-Hour Ambulatory BP Monitoring
- Limited physical exam including height and weight
- Quality of Life Assessment
- Blood assays (serum creatinine, CBC and platelets, renin, aldosterone, BMP and HbA1c)
- Office-based blood sitting and standing pressure (obtained by blinded study personnel) and heart rate
- Medications administered since last visit

- Renal Duplex Ultrasound (DUS) - for subjects who received renal denervation treatment
 - Subjects will be required to have a 6-month duplex ultrasound to assess for evidence of significant stenosis, defined as $\geq 60\%$ as reported by the duplex ultrasound (DUS) core laboratory. A significant stenosis ($\geq 60\%$) detected by DUS will trigger the performance of a confirmatory CTA or DSA.
 - If a diagnostic duplex ultrasound cannot be adequately achieved at the 6-month follow-up, then a CTA or DSA must be conducted.
- Adverse events
- Blinding index assessment

NOTE: Control subjects do not require a duplex ultrasound. Unblinding should occur after all other 6-month follow-up assessments are completed.

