6.7. Device Labeling

The Vessix Reduce Catheter Directions for Use (DFU), Operator's Manual (OM) and packaging are labeled as investigational. Use of these devices outside of this clinical study is strictly prohibited. A copy of the DFUs and OM will be provided in the local language and are included in the study Manual of Operations. The catheter packaging will include peelable, self-adhesive labels for each unit shipped. The labeling will include the following information in English.

- Product Name
- Universal Part Number (UPN)
- Serial or tracking identification number
- Lot number
- Product dimensions
- Expiration (use by) date

7. Objectives

The objective of the REDUCE-HTN: REINFORCE Clinical Study is to assess safety and efficacy of the Vessix™ Renal Denervation System for the treatment of uncontrolled hypertension [off-treatment office systolic blood pressure (OSBP) ≥ 150 mmHg and ≤ 180 mmHg].

8. Endpoints

The endpoints of the study are based upon the safety and efficacy of the Vessix Renal Denervation System.

8.1. *Primary Efficacy Assessment*

The primary efficacy assessment is the mean reduction in average 24-hour ambulatory systolic blood pressure (ASBP) at 8 weeks post randomization.

8.2. *Safety Assessments*

Safety Assessments analyzed at all follow-up time points:

- All-cause death
- Renal failure
- Hospitalization for hypertensive crisis
- Hospitalization due to severe hypotension/syncope

Safety Assessments analyzed at 4 weeks:

- Significant embolic event resulting in end-organ damage or intervention to prevent it
- Renal artery dissection or perforation requiring intervention
- Vascular complications requiring surgical repair, interventional procedure, thrombin injection, or blood transfusion

Safety Assessments analyzed at 6 months:

- Significant new renal artery stenosis assessed by duplex ultrasound (DUS) and confirmed by the angiographic core laboratory [$>70\%$ stenosis by computed tomographic angiography (CTA) or digital subtraction angiography (DSA)] through 6 months post randomization
 - Subjects will be required to have a 6-month duplex ultrasound to assess for evidence of significant stenosis, defined as $\geq 60\%$ as reported by the duplex ultrasound (DUS) core laboratory. A significant stenosis ($\geq 60\%$) detected by DUS will trigger the performance of a confirmatory CTA or DSA.
 - If a diagnostic duplex ultrasound cannot be adequately achieved at the 6-month follow-up, then a CTA or DSA must be conducted.

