Once a subject has signed the IRB approved study informed consent form, and has met all clinical inclusion and no clinical exclusion criteria, the subject will be considered eligible to be enrolled in the trial. If a subject is found to meet exclusion criteria during the angiographic eligibility assessment, the subject will be considered a screen failure and should not be enrolled. If the subject is found to meet the inclusion criteria during the diagnostic angiographic phase of the procedure, he/she should be randomized to Treatment or Control using the Interactive Randomization System at which time the subject is considered enrolled in the study.

11.3. *Withdrawal*

All subjects enrolled in the clinical study (including those withdrawn from the clinical study or lost to follow-up) shall be accounted for and documented. If a subject withdraws from the clinical investigation, the reason(s) shall be reported. If such withdrawal is due to problems related to investigational device safety or performance, the investigator shall ask for the subject's permission to follow his/her status/condition outside of the clinical study.

Reasons for withdrawal may include but are not limited to:

- Physician discretion
- Subject choice to withdraw consent
- Lost to follow-up or death

While study withdrawal is discouraged, subjects may withdraw from the study at any time with or without reason, and without prejudice to further treatment.

Additional data may not be collected after the point at which the subject has been withdrawn from the study, or withdraws his/her consent. All open adverse events should be closed or documented as chronic (ongoing). Data collected up to the point of subject withdrawal may be used.

11.4. *Subject Status and Classification*

Subjects will be classified in the study based upon subject conditions that relate to the subject selection process/consent process or further procedures. The definitions are:

Screen Failure: A subject who has signed the informed consent and undergoes screening evaluation(s), but is found to not meet the eligibility criteria.

Intent: A subject who has signed the informed consent and is randomized/enrolled in the study.

Per-protocol: A subject who meets the eligibility criteria and is randomized/enrolled in the study and received the assigned treatment (renal denervation or masked procedure).

12. Study Methods

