12.1. Data Collection

The visit and data collection schedule for the REDUCE-HTN: REINFORCE Study is provided in Table 12.1-1. Subjects may be followed for up to 36 months but are only required to complete follow up through the 24 month visit.

Table 12.1-1: REDUCE-HTN: REINFORCE Study Data Collection for Scheduled Visits

	Screening / Baseline	RDN and Masked Procedure	Hospital Discharge	2 Wks (14±7 days)	4 Wks (28±7 days)	8 Wks (56 ±7 days)	3 Mon (90 ±14 days)	4 Mon (120 ±14 days)	5 Mon (150 ±14 days)	6 Mon (180 ±14 days)	12 Mon (365 ±30 days)	18 Mon (540 ±30 days)	24 Mon (730 ±30 days)	30 Mon (900 ±30 days)	36 Mon (1095 ±30 days)
Office Seated BP x 3; Standing BP; Heart Rate; Height & Weight; Limited Physical Exam	X		X	X	X	X	X	X	X	X	X	X	X	X ³	X ³
24-hour Ambulatory BP	X				X	X				X	X				
Quality of Life (PGWBI)	X					X				X	X		X		X ³
Renin ²	X					X				X					
Aldosterone ²	X					X				X					
Serum Creatinine	X		X			X				X	X		X		X ³
CBC with platelets, BMP, HbA1c	X		X			X				X	X		X		X ³
Pregnancy Test (as applicable)	X	X													
CTA	X									X ¹			X ⁴		
Renal Angiogram (DSA)		X								X ¹			X ⁴		
Renal Duplex Ultrasound (DUS)										X			X ⁴		
Adverse events assessment		X	X	X	X	X	X	X	X	X	X	X	X	X ³	X ³
Blinding Index Assessment			X			X				X					

¹ A Renal DUS is required for subjects who receive treatment. If DUS shows a ≥60% stenosis per the core laboratory or is inconclusive per the core laboratory after repeat DUS, CTA or DSA are required.

² Renin and Aldosterone Serum tests will be collected at screening/baseline, 8 weeks and 6 months post-randomization. Subjects that are enrolled/randomized prior to the implementation of protocol version AB will not undergo Renin or Aldosterone testing

³ Visit/assessment not required after approval of protocol version AH.

⁴ Only subjects who received treatment and reach the 24 month follow up after approval of protocol version AH will be required to undergo a DUS at 24 months. If the DUS shows a ≥60% stenosis per the core laboratory or is inconclusive per the core laboratory after repeat DUS, a CTA or DSA is required.

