14.2. General Statistical Methods

14.2.1. Analysis Sets

The primary and pre-specified additional assessments will be analyzed on an intent-to-treat (ITT) basis and on a per-protocol basis. For the ITT analysis, all subjects who sign the written ICF and are randomized in the study will be included in the analysis population, regardless of whether the subjects receive the assigned treatment. For the per-protocol analysis, only randomized subjects who meet the eligibility criteria and receive the assigned treatment will be included in the analysis population.

The ITT population will be the primary analysis set for the purpose of assessing superiority of Test to Control for 8-week average 24-hour ASBP reduction. All other endpoint analyses will be based on ITT population.

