14.3. Data Analyses

Baseline data will be summarized by treatment group for the randomized study. Subject demographics, clinical history, procedure assessment, and medication compliance will be summarized using descriptive statistics (e.g., mean, standard deviation, n, minimum, maximum) for continuous variables and frequency tables for discrete variables. The analysis unit may be (but will not be limited to) by subject, catheter, or treatment.

Test and Control in the randomized study will be compared as needed with a Chi-square test or a Fisher exact test for discrete variables and a Student t-Test for continuous variables. The differences between Test and Control in the randomized study and their 95% confidence intervals will be presented as needed.

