	
Through 6 months post randomization:
 
 • Significant new renal artery stenosis >70% assessed by duplex ultrasound (DUS) and confirmed by the angiographic core laboratory [computed tomographic angiography (CTA) or digital subtraction angiography (DSA)]

Orthostatic Hypotension
	
A fall in systolic blood pressure of at least 20 mmHg or diastolic blood pressure of at least 10 mmHg (as compared to sitting blood pressure measurement) within 3 minutes of assuming a standing position²²

Renal Artery Dissection (NHLBI Grade Types)
	
Type A - Small radiolucent area within the lumen of the vessel disappearing with the passage of the contrast material.
 
Type B - Appearance of contrast medium parallel to the lumen of the vessel disappearing within a few cardiac cycles.
 
Type C - Dissection protruding outside the lumen of the vessel persisting after passage of the contrast material.
 
Type D - Spiral shaped filling defect with or without delayed run-off of the contrast material in the antegrade flow.
 
Type E - Persistent luminal filling defect with delayed run-off of the contrast material in the distal lumen.
 
Type F - Filling defect accompanied by total vessel occlusion.

	
NOTE: See Major Adverse Event definition.

Table 27.2-1: Definitions

Term	Definition
Renal Artery Perforation	
Angiographic perforation: perforation detected by clinical site or the Angiographic Core Laboratory at any point during the procedure.
 
Clinical perforation: perforation requiring additional treatment (including efforts to seal the perforation), or resulting in significant hemodynamic compromise, abrupt closure, or death.
 
NOTE: Only clinical perforations will be considered endpoint events.
 
NOTE: See Major Adverse Event definition.

Renal Artery Stenosis	
>70% narrowing in the renal artery as confirmed by CTA or DSA.
 
NOTE: See Major Adverse Event definition.

Renal Failure	
Serum Creatinine increased to more than 300% (>3-fold) from baseline, or more than or equal to 4.0 mg/dL (354 µmol/l) with an acute increase of at least 0.5 mg/dl (44 µmol/L) or on renal replacement therapy.²⁹
 
NOTE: See Major Adverse Event definition.

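### The 6-month renal artery stenosis assessment falls under the ITT rule although only denervated subjects have a scheduled duplex scan, and the synopsis omits the treatment limit on the 24-month scan

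*Combined protocol and SAP*

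**What the plan says.** **Endpoint.** Section 8 (Endpoints) lists new renal artery stenosis among the safety assessments in 8.2. It is detected by DUS, confirmed by the angiographic core laboratory at more than 70% on CTA or DSA, and counted "through 6 months post randomization". The Major Adverse Event entry in Table 27.2-1 uses the same window ("Through 6 months post randomization").

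**Analysis set.** Section 14.2.1 defines ITT as all randomised subjects, treated or not. After naming ITT as the primary set for 8-week ambulatory pressure, it adds: "All other endpoint analyses will be based on ITT population". No safety, as-treated or imaged set is defined.

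**Who is scanned at 6 months.** Footnote 1 of Table 12.1-1: "A Renal DUS is required for subjects who receive treatment". Section 12.11 lists the scan for denervated subjects and adds: "Control subjects do not require a duplex ultrasound". Section 15.3.1 also describes the scans as following denervation. The sub-bullet in 8.2 requires the scan of subjects in general, with no limit by arm.

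**Who is scanned at 24 months.** Footnote 4 of Table 12.1-1: "Only subjects who received treatment and reach the 24 month follow up after approval of protocol version AH will be required to undergo" a DUS. Sections 12.14 and 15.3.1 agree, and 15.3.2 limits the follow-on CTA or DSA in the same way. The Follow-up Schedule row of the synopsis gives the 24-month DUS to everyone not yet through month 24, without mentioning treatment.

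**Comparisons.** Section 14.3: "The differences between Test and Control in the randomized study and their 95% confidence intervals will be presented as needed".

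**The concern.** An endpoint that depends on a scan can be summarised only in people who were due to have it. Under the ITT rule, subjects with no scheduled DUS enter the stenosis denominator. A Control entry of zero would then read as looked for and not found, when no systematic search was made. A difference from Test would mix any effect of the device with the effect of imaging one arm and not the other.

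This matters because stenosis is a safety event in the very vessel the device treats, so readers will look for that row. The synopsis mismatch is a separate matter: a site or analyst working from the synopsis would expect 24-month scans in Controls that the body does not ask for.

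**Working it through.** The plan states no stenosis rate, sample size or precision for this endpoint, so there is no figure to reproduce. The check has a textual part and an illustration of size.

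**1. Does stenosis fall under the ITT sentence?** It is listed in section 8, headed Endpoints, and the sentence in 14.2.1 covers all endpoints other than the primary. Stenosis is not named there, but nothing exempts it.

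**2. Does the per-protocol set avoid the problem?** No. Section 14.2.1 names that set only for the primary and additional assessments. By the definition in 11.4 it also keeps anyone who "received the assigned treatment (renal denervation or masked procedure", so treated Controls stay in, and it has no imaging condition.

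**3. Inputs for size.** 51 randomised (synopsis); 2:1 allocation (14.2.2). The actual split is not given. Assumed: 51 × 2/3 = 34 Test and 51 × 1/3 = 17 Control.

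**4. Control entry.** With 0 events in n, the exact (Clopper-Pearson) 95% upper limit is 1 − 0.025^(1/n).
- n = 17: 1 − 0.025^(1/17) = 19.5%.
- Other splits: n = 21 (30 Test) gives 16.1%; n = 13 (38 Test) gives 24.7%.

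**5. Difference that 14.3 would allow.** The interval method is not stated, so Newcombe's hybrid score interval is assumed. With a Control count of 0 the limits are:
- lower = p − √[(p − l)² + u₀²]
- upper = the Test arm's Wilson upper limit

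Here p is the Test proportion, l its Wilson lower limit, and u₀ the Wilson upper limit for 0/17 (18.4%).

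| Test events | Difference (points) | 95% CI |
|---|---|---|
| 1/34 | 2.9 | −15.6 to 14.9 |
| 2/34 | 5.9 | −13.0 to 19.1 |
| 3/34 | 8.8 | −10.5 to 23.0 |

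The lower limits are driven largely by the Control zero, which rests on no scheduled imaging.

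**6. Could the Test count be above zero?** Section 5.2.1 reports, for this system's single-arm study of 146 treated subjects, one stenosis needing intervention and three others that were flow-limiting. The chance of at least one in 34 is 1 − (1 − p)^34:
- p = 1/146: 21%.
- p = 4/146: 61%.

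Both are rough. The number scanned in that study and the percent narrowing of those lesions are not given, so they may not match the more-than-70% definition used here.

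**7. Test rate.** If all 34 Test subjects are treated and imaged, the ITT and denervated-and-imaged denominators are the same. Two events would be 2/34 = 5.9% (exact 95% CI 0.7 to 19.7%) either way. The documents do not say how many Test subjects were untreated or unscanned, so no size is put on that.

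**The case against.** The strongest reply is that the misleading entry is inferred. No section lays out a by-arm stenosis table, and 14.3 offers differences only as needed. No supplied rule says an unscanned subject counts as event-free, and an endpoint defined by DUS could be read as a proportion of those assessed. Sections 14.3.2 and 14.3.5 refer to a separate Statistical Analysis Plan that is not in the supplied text and may settle the denominator. All of this stands, and it is why the claim is that the plan could produce such an entry. It does not remove the point, because the only rule in the supplied text is ITT.

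Stronger readings are tempting, and the documents do not support them:

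- **A reader might infer that Controls are never examined.** They have adverse-event review at every visit and serum creatinine at discharge, 8 weeks and 6, 12 and 24 months (Table 12.1-1). Core-laboratory DSA covers clinical events (15.3.2), and the events committee adjudicates reported stenosis (24.3). Ascertainment is unequal, not absent.
- **A reader might infer that ITT understates the device's stenosis rate.** Shown by arm, the Test figure does not move if all Test subjects are treated and imaged. Pooling the arms would shrink it by a third (34/51 = 0.67), but nothing calls for pooling.
- **A reader might infer that the 24-month DUS is an endpoint left without a denominator.** The stenosis window ends at 6 months throughout, and the later scan reads as safety surveillance in a stated group. What is missing there is reporting detail.
- **A reader might fear a false positive test.** Section 14.1.1 rules out formal tests.

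**Conclusion.** The point holds, as a minor one. In the supplied text the 6-month stenosis assessment is on ITT while its scheduled scan is for denervated subjects only. A by-arm summary could show about 0/17 for Control (0 to 19.5%) and an optional difference of roughly 3 to 9 points for one to three Test events. Neither would be a fair comparison. The consequence is a misleading table entry and interval; no error rate or power is affected.

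The figures rest on an assumed 34:17 split, assumed event counts and an assumed interval method. The textual finding rests on none of these, though the unseen analysis plan could already resolve the denominator.

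Two wording conflicts also need to be reconciled: the synopsis against Table 12.1-1, 12.14, 15.3.1 and 15.3.2 on the 24-month imaging, and the unrestricted wording in 8.2 against Table 12.1-1 and 12.11 on the 6-month scan.

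**What to change.** In 8.2 and 14.2.1, make new renal artery stenosis an exception to the ITT rule:

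- **Population and summary:** denervated subjects; count and proportion with an exact 95% interval.
- **Numerator:** every confirmed stenosis at any time through 6 months, on scheduled or unscheduled imaging.
- **Denominator:** denervated subjects who had such an event or an interpretable DUS, CTA or DSA for the 6-month assessment. Counting only those imaged at the 6-month visit would lose a stenosis confirmed earlier in a subject with no 6-month scan.
- **Completeness:** state how many denervated subjects were not imaged.
- **Control:** show as 'not systematically assessed', give no Test-Control difference, and list any clinically detected events.
- **Month 24:** summarise DUS findings descriptively among those scanned.

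Reconcile the synopsis with Table 12.1-1, 12.14, 15.3.1 and 15.3.2, and 8.2 with Table 12.1-1 and 12.11. Which imaging rule is right is for the sponsor. If the separate Statistical Analysis Plan already sets such a denominator, carry it into 14.2.1.

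The cost is wording, with no added imaging called for by this change. The interval may be slightly wider if some treated subjects were not imaged, and no between-arm stenosis comparison will be reported.
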